12.6.2.1.3 Particles Suspended in Air

During each Exposure and Non-Exposure Event, there are 2 Dust Trak sensors that measure in real-time suspended particulate matter in air (PM1, PM2.5, PM4 and PM10) every minute. Each sensor was placed at different locations during an event. To assess the change in particulate matter suspended in air between an Exposure and Non-Exposure Event, this will be modelled using a linear model.

The SAS procedure PROC MIXED will be used with the restricted maximum likelihood method for estimation of the parameters. The dependent variable will be the average of the 1 minute readings from the start till end of each event for each sensor. The mixed model will use the mean as dependent variable and the following covariates will be included in the model: location and event type.

The denominator degrees will be the same as describe for the Carbonyls (Section 11.6.2.1.1).

The SAS code for the mixed model to be used is shown below:

```
Proc mixed data=_data_ method=reml;
  Class location event_type;
  Model endpoint = location event_type/ ddfm=kr;
  Lsmeans event_type / diff alpha=0.05 cl;
  Lsmeans location/ diff alpha=0.05 cl;
Run;
```

12.6.2.1.4 Descriptive Analysis of Indoor Air Quality parameters

In addition to the statistical analysis of the indoor air quality parameters described in Sections 12.6.2.1.1 to 12.6.2.1.3. The IAQ parameters (formaldehyde, acetaldehyde, acrolein and crotonaldehyde, 3-Ethenylpyridine (3-EP), Nicotine, NNN, NNK, PM1, PM2.5, PM4 and PM10) and will be summarized by time (where applicable), event number and type of event (Exposure vs Non-Exposure). All IAQ values will be log-transformed (base_e) prior to the analysis except the particulate matter values PM1, PM2.5, PM4 and PM10.

All raw IAQ values except particulate matter variables PM1, PM2.5, PM4 and PM10 generated during an event will be listed. For particulate matter parameters only the mean for each sensor during an event will be listed.

Summary statistics (Section 12.1.2) of the IAQ endpoints will also include the percent change between Exposure and Non-Exposure Event, together with 95% CI for IAQ values having at least 50% of the measured values above the limit of quantification (LOQ).

For each IAQ parameter, a plot will be generated by location and exposure type (Exposure vs Non-Exposure) to assess whether differences exist in exposures at different locations.

For carbonyls, exposure vs time will be plotted with separate colors for location and type of Exposure Event. For TSNAs and tobacco specific markers, exposure vs location will be plotted with separate colors for the event type. Lastly, for particles suspended in air, the mean exposure (averaged over the duration of an event) vs location will be plotted with separate colors for each event type.

12.6.2.2 Assessment of levels of exposure to additional selected HPHCs

Similar to the primary analysis described in 12.6.1.1, for each urinary biomarker of exposure listed in the secondary objective HMPMA, 3-HPMA, S-PMA and HEMA, the change between pre-event and latest post two hour urinary BoExp adjusted for creatinine will be modeled using a linear model in the Compliant Exposure Set. The effect of passive exposure to IQOS aerosol during the Exposure Event on the mean change in levels of urinary BoExp together with the 95% confidence intervals (CIs). Other contrasts can be constructed to determine the change in urinary BoExp for participants with other smoking status after passive exposure to IQOS usage.

A descriptive analysis of these same biomarkers will be performed as well as detailed in Section 12.6.1.2.

12.6.2.3 Analysis of the Active Exposure Group

To quantify the change between the pre-event and end of study urinary BoExp levels in IQOS Active Users. The change from baseline adjusted for creatine is the dependent variable with baseline, Sex, number of *HeatSticks*, duration of exposure and IAQ parameters (Section 8.2.1) as the covariates. Similar to Section 12.6.1.1, an air quality covariate related to each BoExp is included in the model depending on the endpoint and is described in Appendix 15.2. The same IAQ covariates listed for the

various BoExp is also assessed using a step-down regression approach in the following algorithm. Fit a full model with all covariates

1. Drop one IAQ covariate and re-fit the model.
2. Perform a likelihood ratio test and drop the IAQ covariate with the largest p-value for the likelihood ratio statistic if it is more than 0.05.
3. Repeat steps 2 and 3 until no more IAQ covariates can be dropped.
4. Refit the final model with the IAQ covariates remaining in the model and estimate exposures for the Active IQOS group

An example of the SAS code is shown below,

```
Proc mixed data=_data_ method=reml;
Class sex heatsticks;
Model endpoint = baseline sex heatsticks duration <IAQ covariates> / ddfm=kr;
estimate 'Active' intercept 1 baseline xx sex 0.5 0.5 heatsticks xx duration xx
IAQ1 xx ... IAQn xx / alpha=0.05 cl;
Run;
```

We define xx are the mean of a continuous covariate for participants in the active Exposure Group across all Exposure Events. For air quality covariates, xx is the mean calculated over all Exposure Events.

The LSmeans and corresponding confidence intervals will be exponentiated, back-transformed to the original scale and reported as geometric means with its confidence intervals.

Descriptive statistics and figures of each BoExp for the actively exposed participants will be summarized in the same way as described in Section 12.6.1.2. However, the results will only be stratified by Sex.

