#### 6.2.1 From Screening to Event Participation

There are no restrictions on use of IQOS or cigarettes or any other tobacco or nicotine-containing products during screening until participation in any of the events.

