## 6.6 Restrictions

### 6.6.1 General Restrictions

As the study objective is to represent a real life setting, no restrictions apply to any of the participants other than stated in the Inclusion/Exclusion criteria (i.e., with regards to smoking prior to the events, wearing perfume, dress code, etc.)

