#### 12.5.1 Analysis of the Active Exposure Group

The primary endpoints will look at the change between the pre-event urinary BoExp and latest post two-hour urinary BoExp observation. A linear mixed effects model with IAQ, duration of exposure (time between pre-event collection and last post exposure collection) and number of sticks used during the event, will be modelled as fixed effects with a random subject effect. Other covariates or interaction terms may be added as needed. Appropriate contrasts will be constructed to determine the effect of active exposure to IQOS usage during the Exposure Event on the mean change in levels of urinary BoExp to selected tobacco specific HPHCs together with the 95% confidence intervals (CIs).

---

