7.1.3 Step 3: Exposure Events

This step comprises the Exposure Events which will occur in the same restaurant setting as the Non-Exposure Events in order to control for restaurant-related exposures (i.e., location, air ventilation and table setting) that could confound study results. The first of the Exposure Events will occur within 4 weeks of the Non-Exposure Events. The Exposure Events will replicate the meal, beverages and restaurant dynamics of the Non-Exposure Event.

Exposure Event participants may or may not have attended a Non-Exposure Event. Participants attend the dinner Event at no cost to themselves. The participants who attend more than one event will represent the same product use phenotypes for both events, except the IQOS Users will be assigned for the Exposure Events to either a) an IQOS Active User, or b) an IQOS Passive User (see [Table 1](#)).

The Exposure Events will include a minimum of 169 passively exposed participants. During each Exposure Event a total of $20\% \pm 5\%$ of the available seats at the Event location will be allocated to IQOS Active Users (who use IQOS during the event). The remaining seats will consist of passively exposed participants with the following product use phenotypes: 50% ($\pm 5\%$) Non-Smokers, 25% ($\pm 5\%$) IQOS Passive Users who refrain from using any nicotine or tobacco product, and 25% ($\pm 5\%$) Cigarette Smokers who refrain from using any nicotine or tobacco products.

IQOS Active Users will enter the event location first and start using IQOS *ad-libitum* for 1h prior to the other participants (passive Exposure Group) entering the event location.

IAQ measurements will be sampled for up to 3h prior to the start of the Event and for 3h after the last participant was exposed for 1h. Urine specimens per person will be collected for analysis as follows:

The first urine sample will be collected prior to the start of the event. For the second urine sample, collection will only start with the first void after 2 hours of IQOS exposure to allow sufficient exposure to have occurred and therefore detection of BoExp in the urine. From the 2h time point onwards every subsequent void will be collected and the previous urine sample discarded with the last void collected ideally at the end of the 4h exposure period. Only the first and the last urine sample taken will be analyzed.

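### The Active Exposure analysis gives a within-group change in continuing IQOS users, which reflects event use relative to usual use and not the effect of active exposure that the protocol promises

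*SAP*

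**What the plan says.** **Promised.** Protocol 12.5.1: "Appropriate contrasts will be constructed to determine the effect of active exposure to IQOS usage during the Exposure Event on the mean change" in urinary biomarkers. The model given there is nonetheless a one-group model.

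**Delivered.** SAP 12.6.2.3 aims "To quantify the change between the pre-event and end of study urinary BoExp levels in IQOS Active Users". The model has baseline, sex, number of HeatSticks, duration and air-quality covariates, with no group or event-type term. The last step is to "estimate exposures for the Active IQOS group", through one ESTIMATE row called 'Active', which is then exponentiated. Descriptive results are split by sex only. Post-hoc section 14.5.2 refits the same model without HeatSticks and adds no comparator. SAP section 10, on changes from the protocol, mentions only the removal of the random subject effect.

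**Use before the event.** Protocol 6.2.1: "There are no restrictions on use of IQOS or cigarettes or any other tobacco or nicotine-containing products during screening until participation". Protocol 6.6.1: "no restrictions apply to any of the participants other than stated in the Inclusion/Exclusion criteria (i.e., with regards to smoking prior to the events". SAP 5.2 takes baseline just before entry to the event room. IQOS Users are daily users by definition (SAP Table 2), and use at the event is ad libitum (Protocol 6.2).

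**Possible comparator.** The Exposure Events also seat "IQOS Passive Users who refrain from using any nicotine or tobacco product" (SAP 7.1.3). They give the same two voids (SAP 11.2) but enter only the Compliant Exposure Set model.

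**The concern.** A pre-to-post change equals an effect of use only if, without use, the level would have stayed at baseline. In daily users who arrive after unrestricted use it would not: an abstaining user's level falls. The change in Active Users therefore compares use at the event with the same person's use beforehand. It does not compare use with non-use.

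At stake is the reading of one table. A flat 'Active' row could be taken to mean that using IQOS at the event adds little to urinary biomarkers, when it may only mean that people carried on as usual. The wording of Protocol 12.5.1 invites that reading. So does the SAP 3.0 revision note, which presents 14.5.2 as estimating the effect of no HeatSticks use; dropping the covariate still averages over people who used HeatSticks.

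The SAP met a related gap in the passive analysis. Section 14.1 says the planned model did not compare event types and adds a contrast. The Active analysis received none.

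**Working it through.** The plan states no figure for this analysis, so there is none to reproduce. The documents give no biomarker half-life, no SD and no ratio of event use to usual use; values for these are assumptions.

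**1. What each quantity estimates.** Assume first-order elimination and steady state before the event. Let T be the half-life, t the elapsed time, e = 2^(−t/T), and r = event use rate / usual use rate.
- Active Users: post/pre = e + r(1 − e)
- Abstaining IQOS Users: post/pre = e (ignoring passive uptake)
- Active/Passive ratio = [e + r(1 − e)]/e

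At r = 1 the Active post/pre is e + 1 − e = 1.00 for every T and t.

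| T (h), t = 4 h | Abstainers | Active, r = 0.5 | Active, r = 1 | Active, r = 1.5 | Active/Passive, r = 1 |
|---|---|---|---|---|---|
| 4 | 0.500 | 0.750 | 1.00 | 1.250 | 2.00 |
| 8 | 0.707 | 0.854 | 1.00 | 1.146 | 1.41 |
| 16 | 0.841 | 0.920 | 1.00 | 1.080 | 1.19 |
| 24 | 0.891 | 0.945 | 1.00 | 1.055 | 1.12 |
| 48 | 0.944 | 0.972 | 1.00 | 1.028 | 1.06 |
| 240 | 0.989 | 0.994 | 1.00 | 1.006 | 1.01 |

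The three Active columns are what the planned row would show. They move with r around 1.00. The last column is the comparison with non-use.

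**2. Group sizes.** Active: 20% of 96 seats (SAP Table 1) × 4 Exposure Events (SAP 12.6.2.1.1) = 76.8, about 77. With three Exposure Events, as Protocol Table 5 appears to show, 57.6, about 58. IQOS Passive: 25% of 169 = 42.

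**3. Precision of the contrast.** SE = SD × √(1/n₁ + 1/n₂), with an assumed log-change SD of 0.5.
- 77 v 42: 0.5 × √(1/77 + 1/42) = 0.096; exp(1.98 × 0.096) = 1.21
- 58 v 42: 0.5 × √(1/58 + 1/42) = 0.101; exp(1.98 × 0.101) = 1.22

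Applying ×/÷ 1.21 (power is two-sided at 0.05):

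| T (h) | Ratio | 95% CI | Power |
|---|---|---|---|
| 8 | 1.41 | 1.17 to 1.71 | 0.951 |
| 16 | 1.19 | 0.98 to 1.44 | 0.439 |
| 24 | 1.12 | 0.93 to 1.36 | 0.225 |

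Two of the three intervals include 1. The formula ignores any loss from limited overlap in elapsed time.

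**4. Why one time slope will not do.** On the log scale abstainers fall by ln 2/T per hour (0.693/8 = 0.087 at T = 8 h), while users at r = 1 have slope 0. At r = 1.5 and T = 8 h, Active Users rise from 1.146 at 4 h to 1.25 at 8 h. A common slope fits neither group. Protocol 4.4 puts the passive stay at about 4 h (not over 5 h) and active use at up to 8 h, so the groups may also differ in elapsed time.

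**The case against.** **The analysis is peripheral.** No listed objective concerns the effect of active use; the Active Users are there to create the aerosol, and there are no formal hypotheses. This stands. The primary conclusions do not depend on this point.

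**The SAP states its aim openly.** It says that it quantifies a change and does not call its row an effect. This stands for the SAP. The protocol does speak of contrasts and an effect, so the two need to be reconciled, at least by a label.

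**HeatSticks is in the model.** It is presumably meant as dose information. But a dose relation within users is not a comparison with non-use, and the example code lists HeatSticks under CLASS, which gives no slope, and requests no HeatSticks effect.

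**The comparator can be read from another table.** The primary model can give the IQOS Passive Users' change, so a reader could set the two rows side by side. True, but no ratio or interval would be reported, and the models adjust differently.

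**A stronger reading.** A reader might infer that the planned estimate is biased toward no effect. The documents do not support that as a general statement. It requires use at the usual rate near steady state, and ad libitum use with an hour of priming and a long stay could move the row either way.

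**Conclusion.** The point holds. The 'Active' row is a within-group change in continuing users and does not deliver the effect of active exposure in Protocol 12.5.1. No planned or post-hoc model compares Active with abstaining IQOS Users.

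Under use at the usual rate near steady state, the row shows 1.00 where the 4 h contrast would be 1.41, 1.19 or 1.12 (assumed half-lives 8, 16, 24 h). If event use differs from usual use, the row tracks that difference.

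It would also be tempting to infer that the contrast settles the question. It does not: at the assumed SD, ratios of 1.19 and 1.12 would have intervals that include 1, and at a half-life of 240 h the contrast itself is only 1.01. It is supportive evidence. The change is worth making, but the study's listed objectives do not rest on it.

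**What to change.** 1. Keep the 'Active' row in SAP 12.6.2.3 and label it *within-group change in continuing users; not an effect of use*. Relabel the 14.5.2 row in the same way.
2. Add a supportive model of log change in all IQOS Users at Exposure Events (Active plus IQOS Passive) with event, group, log baseline, sex, elapsed time from pre-event to last void, and group-by-elapsed-time.
3. Report the Active/IQOS Passive ratio with 95% CI for each biomarker at a common elapsed time where both groups have data, for example about 4 h. Show each group's elapsed-time distribution.
4. State the limits with the result: post hoc (SAP 3.0 already adds analyses after results were reviewed), non-randomised (the Active group is filled first, SAP 7.3.1), a comparator that is itself passively exposed, possibly limited overlap in elapsed time, and modest precision.

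**Cost.** SAP wording and one extra model per biomarker, on data already collected. If elapsed times hardly overlap, the contrast should be reported as not estimable at a common time rather than extrapolated. The relabelling alone removes most of the risk of misreading.

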8.4 Recording of IQOS Use

At each Exposure Event, the IQOS Active Users, will be provided with a personalized ashtray. IQOS *HeatSticks* that are used during the event will be collected in the ashtray and will be collected at approximately 1 hour intervals and recorded by the study personnel to evaluate the total number of *HeatSticks* used per participant during the Exposure Event.

For the analysis of the IQOS Active User Group, the number of *HeatSticks* used by a participant is defined as all *HeatSticks* used from the start of first use during priming until the end of the event.

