12.1.3 Definitions for Statistical Data Analysis

12.1.3.1 Categorical Variables

Categorical variables used in this study are shown in [Table 5](#) below.

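### In SAP 12.6.2.3 the example code makes the HeatStick count a class variable but estimates at its mean, so the HeatStick-adjusted 'Active' estimate cannot be computed as printed

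*SAP*

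**What the plan says.** SAP 12.6.2.3 models the change in each urinary biomarker in IQOS Active Users, with baseline, sex, number of HeatSticks, duration of exposure and air-quality terms as covariates. The example code contains:

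- the class statement, "Class sex heatsticks";
- the model, "Model endpoint = baseline sex heatsticks duration <IAQ covariates> / ddfm=kr";
- the estimate, "estimate 'Active' intercept 1 baseline xx sex 0.5 0.5 heatsticks xx duration xx", which ends "IAQ1 xx ... IAQn xx / alpha=0.05 cl".

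The text under the code explains the coefficients: "We define xx are the mean of a continuous covariate for participants in the active Exposure Group across all Exposure Events".

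Elsewhere, SAP 8.4 derives the variable as a count per person: "the number of *HeatSticks* used by a participant is defined as all *HeatSticks* used from the start of first use during priming", running to the end of the event. SAP 12.1.3.1 introduces Table 5 with "Categorical variables used in this study are shown in"; that table lists Sex, Event Type and Product Use Status only. The post-hoc HeatStick models in 14.2 and 14.5.1 leave the cumulative count out of their CLASS statements.

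**The concern.** One variable has two roles in the same block of code. Sex, a true class variable, receives one ESTIMATE coefficient per level (0.5 and 0.5). HeatSticks, also in CLASS, receives a single coefficient equal to a mean, which makes sense only for a continuous covariate.

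At stake is the model-based estimate for active users, planned for every biomarker in Table 15.2.2.6.1. SAP 14.5.2 depends on it too, because it refits this model without HeatSticks to show what the adjustment does.

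There is also a risk of an improvised repair. The text speaks of exponentiating LSmeans, although the code has no LSMEANS statement. An analyst who met a non-estimable result and switched to LSMEANS with HeatSticks still in CLASS would get a number without warning. It would average equally over every distinct count, including counts held by one person, and would not be the estimate at the mean count.

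**Working it through.** The documents state no figure for this analysis, so there is nothing to reproduce. The check is whether the printed ESTIMATE row is an estimable function of the printed model.

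**1. Algebra (no assumption about counts).** Let the count take k distinct values. With HeatSticks in CLASS, each participant's row of the design matrix X has 1 in the intercept column and exactly one 1 among the k HeatStick columns. Take the vector v with 1 for the intercept, −1 for each HeatStick column and 0 elsewhere. Then Xv = 0. A row L is estimable only if Lv = 0, that is

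1 − (sum of the HeatStick coefficients) = 0.

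The printed row supplies one HeatStick coefficient, the mean count h̄, and the other levels get 0. The condition becomes 1 − h̄ = 0, so h̄ must equal exactly 1. It does not matter which level receives h̄. The same test for sex gives 1 − (0.5 + 0.5) = 0, which passes.

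**2. Numerical confirmation.** Inputs from the documents: 96 seats and 20% ± 5% active users (SAP Table 1), read as percentage points, give 14.4 to 24 per event. SAP 12.6.2.1.1 names four Exposure Events; protocol Table 5 appears to plan three. The range is therefore 3 × 14.4 = 43.2 to 4 × 24 = 96 users, with 4 × 19.2 = 76.8 in the middle. The simulations used whole numbers per event: 14 × 3 = 42, 19 × 4 = 76 and 24 × 4 = 96.

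Assumption, because the documents give no HeatStick distribution: Poisson counts with mean 5, 10 or 15. One air-quality term was included. Each of the nine combinations was run 200 times, testing whether L·(X⁻X) = L.

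| Coding | 'Active' estimate estimable | df used by HeatSticks |
|---|---|---|
| CLASS, as printed | 0 of 200 in all nine scenarios | 9 to 17 (medians; 10 to 18 levels) |
| Continuous | 200 of 200 in all nine scenarios | 1 |

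**3. Cost if CLASS were kept (illustrative only).** Intercept, baseline, sex, duration and one air-quality term use 5 df. One simulated data set with n = 76 and a mean count of 9.51 had 14 levels:

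- CLASS: 76 − 5 − 13 = 58 residual df.
- Continuous: 76 − 5 − 1 = 70 residual df.

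Across scenarios, a median of 2 to 5 levels were held by a single participant. Giving the levels equal weights makes the estimate computable, but it targets a different quantity. Its standard error was about 1.25 to 1.6 times that of the continuous model (scenario medians).

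**The case against.** The code is offered as an example, and everything around it is consistent with a continuous count: the covariate list, the definition of xx, SAP 8.4, Table 5 and the other HeatStick models. A competent programmer would see the non-estimable message on the first run and find the correction in the same section. The printed code yields no plausible wrong number. The analysis is secondary, the study has no formal hypotheses, and the main population is the Compliant Exposure Set. All of this stands and limits the severity.

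It does not remove the point. SAP 14.4 records that another specification error in this plan, in the air-quality models, stopped the specified model from converging, and that the CRO's results came from a different model. Example code in this study has therefore affected what was delivered. The revision history also shows that the code for this section was edited in version 2.0 to remove location, yet the current text still has HeatSticks in CLASS.

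A reader might go further and infer that the Active Exposure Set analysis yields nothing, or that a planned HeatStick slope is lost. The documents support neither reading. The model still fits, descriptive statistics and figures are planned separately, and the 14.5.2 model uses only sex as a class variable and is estimable. SAP 12.6.2.3 asks for no slope; HeatSticks is there as an adjustment covariate.

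**Conclusion.** The code is wrong as written, and this is certain: it follows from the printed statements without any assumed data. The consequence is confined to the HeatStick-adjusted 'Active' estimate for Table 15.2.2.6.1 and the comparison with and without HeatSticks in 14.5.2.

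The level counts, residual df and standard-error ratios rest on assumed Poisson counts. They apply only if someone keeps the count in CLASS, which the SAP text does not propose, so they should not be quoted as a loss built into the plan. Nor do the documents show that any reported result is wrong; they do not say which coding was run. Severity is minor to moderate: worth correcting, but no threat to the primary analysis.

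**What to change.** In SAP 12.6.2.3, change the class statement to `Class sex;` and add a sentence saying that the number of HeatSticks per participant is a continuous covariate. With no other change, the estimate at the mean count becomes estimable and the term uses 1 df. If categories were intended, define them and give one coefficient per level, summing to 1.

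Confirm, and state in the study report, that the continuous coding produced Table 15.2.2.6.1 and the HeatStick-adjusted side of the 14.5.2 comparison. If it did not, rerun the model for each biomarker. The cost is one word of code, one sentence of text and a check of the program behind one table. No new data are needed.
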